### 11.1 Criteria for Study Treatment Discontinuation

Patients will receive study treatment (pralatrexate or observation) until one of the following criteria for study treatment discontinuation applies:

- Development of PD
- Initiation of RT or systemic chemo/biological therapy for treatment of PTCL
- Receipt of systemic steroids > 10 days, with the exception of those as stated in exclusion criterion #5 (see [Section 8.4](#))
- Development of an AE that interferes with the patient's participation
- Lost to follow-up
- Patient decision
- Investigator decision
- Sponsor decision

In addition, for those patients randomized to the Pralatrexate Arm, additional pralatrexate treatment discontinuation criteria are:

- 3 or more consecutive doses of pralatrexate omitted or more than 28 days between doses of pralatrexate
- Treatment with pralatrexate for 2 years

Patients will be seen for the Initial Follow-up Visits as outlined in [Section 10.7](#).

If an investigator feels that a patient would continue to benefit from pralatrexate therapy after completion of 2 years' therapy, they should discuss with the sponsor's medical contact and agree whether or not it is appropriate to continue treatment.

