### 15.8.1 Adverse Events

The Medical Dictionary for Regulatory Activities (MedDRA) will be used to code all AEs to a system organ class (SOC) and a preferred term. Patient incidence of AEs will be tabulated by SOC, preferred term, and severity grade for all AEs, SAEs, treatment-related AEs, and treatment-related SAEs. Each of these outputs will include tabulation by maximum severity for each SOC and preferred term as reported by the investigator based on CTCAE, Version 4.0. If an AE cannot be graded based on CTCAE, the investigator will assign a severity based on 1 = mild, 2 = moderate, 3 = severe, 4 = life threatening, and 5 = death related to AE. Summaries of AEs, SAEs, treatment-related AEs, and treatment-related SAEs occurring in at least 5% of the patients will be provided in descending order of frequency by SOC and preferred term.

Additional tables summarizing patient incidence (by preferred term) of the following will be generated:

- All AEs
- SAEs
- Treatment-related AEs
- Treatment-related SAEs
- Grade 3 or higher AEs
- AEs leading to the discontinuation of pralatrexate or observation or removal from study
- AEs leading to dose reductions of the study drug
- AEs with incidence  $\geq 5\%$
- Deaths

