6.2 Safety Analysis Set

The safety analysis set consists of all patients randomized to the Pralatrexate Arm who receive at least 1 dose of pralatrexate plus all patients randomized to the Observation Arm who do not discontinue study within 3 days of randomization. This analysis set will be used for the primary analyses of all safety endpoints.

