8.6 Safety Analyses

Analysis of safety will be performed on the safety analysis set. Study data will be monitored on an ongoing basis by the clinical study team including the medical monitor and the clinical drug safety team's routine activities to ensure patients' safety.

Adverse Events

The Medical Dictionary for Regulatory Activities (MedDRA) will be used to code all AEs to a system organ class (SOC) and a preferred term. Patient incidence of AEs will be tabulated by SOC, preferred term, and severity grade for all treatment-emergent AEs, serious adverse events (SAEs), treatment-related AEs, and treatment-related SAEs. Each of these outputs will include tabulation by maximum severity for each SOC and preferred term as reported by the investigator based on Common Terminology Criteria for Adverse Events (CTCAE),

Version 4.0. If an AE cannot be graded based on CTCAE, the investigator will assign a severity based on 1 = mild, 2 = moderate, 3 = severe, 4 = life threatening, and 5 = Death related to AE. Summaries of AEs that are treatment-emergent, SAEs, treatment-related AEs, and treatment-related SAEs occurring in at least 5% of the patients will be provided in descending order of frequency by SOC and preferred term.

Additional tables summarizing patient incidence (by preferred term) of the following will be generated:

- All AEs;
- SAEs;
- Treatment-related AEs;
- Treatment-related SAEs;
- Grade 3 or higher AEs;
- AEs leading to the discontinuation of pralatrexate or removal from study;
- AEs leading to dose reductions of the study drug;
- AEs with incidence $\geq 5\%$; and
- Deaths.

Adverse Events Grouped by Similar Preferred Term

Summary tables of treatment emergent, treatment-related, serious, and serious treatment-related AEs grouped by similar preferred term will be presented. For this presentation, certain similar preferred terms were identified and coded to the same preferred term in order to present the event in a uniform manner. Terms are presented in [Table 11.1](#) of Appendix 11.4 (additional preferred terms may be identified within each category during data review and added to this list).

Separate outputs will be provided for subgroups defined by age group (< 65 and ≥ 65), gender, and race (if feasible).

Detailed listings for all AEs and listings and/or narratives will be provided for serious and significant AEs and deaths (with “on-study” deaths [deaths that occur before the end of safety follow-up period] identified).

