Overall Summary of Treatment Emergent AEs – Safety Analysis Set	High-level summary of treatment-emergent, serious, treatment-related, and serious treatment-related AEs. Only include treatment-emergent AEs (this applies to all AE tables).
Treatment-emergent AEs – Safety Analysis Set	Summary by SOC and preferred term for each treatment group.
Treatment-emergent AEs Grouped by Similar Preferred Term – Safety Analysis Set	Summary by preferred term for each treatment group, where selected AEs are grouped by similar preferred term as indicated in the appendix.
Treatment-emergent SAEs – Safety Analysis Set	Summary by SOC and preferred term for each treatment group.
Treatment-emergent SAEs Grouped by Similar Preferred Term – Safety Analysis Set	Summary by preferred term for each treatment group, where selected AEs are grouped by similar preferred term as indicated in the appendix.
Treatment-emergent AEs Grouped by Similar Preferred Term Leading to Treatment Discontinuation – Safety Analysis Set – Pralatrexate Arm	Summary by preferred term.
Treatment-emergent AEs by Age Group – Safety Analysis Set	Summary by SOC and preferred term for each age group (< 65, ≥ 65).
Treatment-emergent AEs by Gender – Safety Analysis Set	Summary by SOC and preferred term for each gender.
Treatment-emergent AEs by Race – Safety Analysis Set	Summary by SOC and preferred term for each race (if feasible).
Time to worsening of B-symptoms/Pruritus – Safety Analysis Set	Analysis using the Cox model of time to worsening of B-symptoms/pruritus.
Hematology – Safety Analysis Set	Summary of hematology parameters at baseline, last observed value, maximum observed value, and minimum observed value. Include change from baseline to maximum observed value, minimum observed value and last observed value.
Hematology Shift in Severity – Safety Analysis Set	Tables of shifts in severity from baseline for selected laboratory parameters and selected time points.
Serum Chemistry – Safety Analysis Set	Summary of serum chemistry parameters at baseline, last observed value, maximum observed value, and minimum observed value. Include change from baseline to maximum observed value, minimum observed value, and last observed value.

Title	Description
Chemistry Shift in Severity – Safety Analysis Set	Tables of shifts in severity from baseline for selected laboratory parameters and selected time points.

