ECOG Performance Status – Safety Analysis Set	Summary of ECOG performance status results at each scheduled time-point and the change from baseline.
Concomitant Medications – Safety Analysis Set	Summary of administered concomitant medications by ATC code and preferred term.

FAS = full analysis set HR = hazard ratio SOC = system organ class
PFS = progression-free survival K-M = Kaplan Meier SAE = serious adverse event
OS = overall survival ORR = objective response rate ATC = Anatomical Therapeutic Chemical
CI = confidence interval AE = adverse event ECOG = Eastern Cooperative Oncology Group

Table 9.2. Planned Listings

Title	Description
Patient Accountability	Listing of all patients and the analysis set inclusion information.
Patient Withdrawal	Listing of all patients who withdraw from the study, including the reason for withdrawal and the time of withdrawal.
Protocol-specified Treatment Administration	Listing of all patient protocol-specified treatment administration information.
Adverse Events	Listing of all reported AEs by patient.
Serious Adverse Events	Listing of all patients with at least 1 reported SAE. Only the AEs identified as serious will be included. Listing will include patient number, SOC, and preferred term of AE, date of onset, date of resolution, CTCAE Grade, action taken, and outcome.
Deaths – Safety Analysis Set	Listing of deaths that occur within 30 days of the last dose of protocol specified treatment, including cause of death.
Adverse Events Leading to Protocol-specified Treatment Discontinuation	Listing of all patients who discontinue protocol-specified treatment due to an AE. The listing will include the AE, date of onset of the AE, date of resolution of the AE, severity of AE, and the CTCAE severity grade of the AE.
Hematology	Listing of all hematology parameters.
Serum Chemistry	Listing of all serum chemistry parameters.
Electrocardiograms	Listing of all ECG results, including heart rate, QRS, PR, QT, and QT _c intervals.
Concomitant Medications	Listing of all concomitant medications including the ATC code and preferred term.
ECOG Performance Status	Listing of ECOG performance status at each assessment.
Lesion Measurements	Listing of all lesions at each time-point, including the sum of all target lesions and change from baseline and percent change from baseline.
Efficacy Parameters	Listing of all efficacy parameters for each patient, including survival time, objective response, and PFS time.

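### Two SAP safety outputs, AEs leading to discontinuation and the death listing, are not correctly specified for the Observation Arm

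*SAP*

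**What the plan says.** **AEs leading to discontinuation.** Protocol 15.8.1 plans a by-preferred-term incidence table of "AEs leading to the discontinuation of pralatrexate or observation or removal from study". The corresponding item in SAP 8.6 reads "AEs leading to the discontinuation of pralatrexate or removal from study". SAP Table 9.1 also plans a version with similar terms grouped, whose title ends "Leading to Treatment Discontinuation – Safety Analysis Set – Pralatrexate Arm". SAP Table 9.2 adds a "Listing of all patients who discontinue protocol-specified treatment due to an AE", with no arm named. Protocol 11.1 applies one of its criteria, "Development of an AE that interferes with the patient's participation", to both arms.

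**Deaths.** SAP Table 9.2 plans a death listing for the safety analysis set, defined as "Listing of deaths that occur within 30 days of the last dose of protocol specified treatment, including cause of death". Under SAP 6.2 that set includes "all patients randomized to the Observation Arm who do not discontinue study within 3 days of randomization". SAP 8.6 asks for listings and/or narratives of deaths with on-study deaths flagged, and defines those as "deaths that occur before the end of safety follow-up period". It also plans a deaths table.

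**The concern.** Safety is the trial's secondary objective, and observation is the only comparator. How often patients stop because of an adverse event, and which events are responsible, is a central tolerability measure for a drug given for up to two years to patients already in response. The protocol planned to show this for both arms. The SAP presents itself in its Section 1 as giving the detail of the protocol's analyses, yet it narrows this table without giving a reason.

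The death listing has a different fault. It is titled for a two-arm population, but its selection rule counts from an event that occurs in only one arm. A programmer would have to invent a rule for observation patients or leave them out, and neither choice is documented.

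**Working it through.** No power, alpha or event-count formula applies, so the check compares the texts and follows a patient through them.

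**Step 1: an observation patient who stops for an AE.** Under Protocol 11.1 the patient meets a discontinuation criterion. Under Protocol 10.8 all randomized patients are still followed to progression and then for survival, so stopping observation is not the same as leaving the study. This patient would therefore appear as follows:

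- Protocol 15.8.1 table: included.
- SAP 8.6 table: excluded. Pralatrexate was not stopped, and the patient was not removed from study.
- SAP Table 9.1 grouped-term table: excluded by its title.
- SAP 8.2 and the Table 9.1 disposition table: included, but as a reason category without AE terms.
- SAP Table 9.2 listing of AE discontinuations: possibly included. It depends on whether protocol-specified treatment covers observation, which the SAP does not define.

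No SAP output therefore compares the arms by preferred term for AEs leading to discontinuation.

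**Step 2: the death listing.** The population includes observation patients, but the selection rule needs a last dose. SAP 5.2 and the treatment-administration part of SAP 8.6 use the term protocol-specified treatment in connection with pralatrexate cycles and doses. Protocol 11.1 counts observation as study treatment, but observation still has no dose. SAP 5.2 sets study day 1 for the Observation Arm (randomization plus 3 days) and defines no stop date. SAP 11.3 nevertheless relies on a treatment stop day for post-treatment cut-offs.

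**Step 3: the windows side by side.**

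| Place | Counted from | Length |
|---|---|---|
| SAP Table 9.2, death listing | last dose | 30 days |
| SAP 3, safety follow-up, all patients | discontinuation criteria met | 35 (± 5) days |
| Protocol 7.3, pralatrexate | last dose | 35 (± 5) days, or longer until related AEs settle |
| Protocol 7.3, observation | discontinuation criteria met | 35 (± 5) days |
| Protocol 14.3.1, AE recording on observation | discontinuation criteria met | 30 days |

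With both counted from the last dose, as in Protocol 7.3, the listing stops 35 − 30 = 5 days before the nominal end of follow-up. At the visit-window limits the gap is (35 − 5) − 30 = 0 days to (35 + 5) − 30 = 10 days. It is longer if a related AE keeps follow-up open. A pralatrexate death on day 33 can therefore be on-study under SAP 8.6 and absent from the listing. SAP 3 and Protocol 7.3 also disagree on where safety follow-up ends for pralatrexate patients.

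**Step 4: size.** The planned Observation Arm is 183 of 549 patients: 183/549 = 33.3%. This is an upper bound on the patients who could fall outside the two outputs, because SAP 6.2 already removes those who leave within 3 days. The documents give no rate of death or AE discontinuation on observation, so the number of affected events cannot be derived.

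**The case against.** The strongest reply is that little is lost. SAP 8.6 says its tables will be produced, and they include a deaths table on the safety analysis set. It also requires listings and/or narratives of deaths with the on-study flag. A death is a serious adverse event under Protocol 14.6.1, reportable on observation until 30 days after discontinuation criteria are met (Protocol 14.6.2), and the SAE listing in SAP Table 9.2 has no arm limit. Every death is also an OS event. Reasons for discontinuation are summarised without arm restriction. SAP Section 9 offers its outputs as ones that could be provided, with shells to follow. Thirty days is not arbitrary either: it matches the recording windows for AEs, SAEs and medications, and a 30-day listing can coexist with an on-study flag.

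Most of this stands. A reader might infer that the SAP leaves observation deaths and AE discontinuations uncounted, or would report them as zero. The documents do not support that, because the outputs just named capture both. A reader might also infer that the drug would look worse than it is. But a table labelled as one-arm gives no comparison; it does not report zero for the control.

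The reply does not restore the by-preferred-term comparison that the protocol planned, because disposition reasons carry no AE terms. Nor does it give the death listing a rule for observation. Table 9.1 contains no deaths table, so Section 9 does not carry through the one in SAP 8.6, and this listing is the only Section 9 output stated to give cause of death.

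**Conclusion.** The point holds as a minor specification fault in two outputs. The SAP departs from Protocol 15.8.1 by dropping observation from the table of AEs leading to discontinuation. Its Table 9.2 death listing is undefined for observation patients and does not match the on-study definition in SAP 8.6. It is better called undefined than an exclusion, because the SAP never says what protocol-specified treatment covers.

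Up to 183 of 549 patients (33%, less early leavers) are affected on a literal reading. That reading assumes that the planned arm sizes are reached and that the term means pralatrexate. A reader might try to estimate missed deaths by assuming a survival time after observation ends. The documents give none for this population; the median OS of 14.5 months in Protocol 4.1.1 comes from treated relapsed or refractory patients. No count is offered here. Primary analyses, alpha, power and sample size are unaffected.

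**What to change.** 1. In SAP 8.6, restore observation to the item on AEs leading to discontinuation, as in Protocol 15.8.1. Show the grouped-term table in Table 9.1 by treatment group.
2. In Table 9.2, tie the death listing in both arms to the on-study definition in SAP 8.6. Count from the last pralatrexate dose, or from the date discontinuation criteria are met on observation.
3. Define protocol-specified treatment and an Observation Arm stop date in SAP 5.2; the stop date also serves the cut-offs in SAP 11.3. Protocol 10.5 limits observation visits to two years, while Protocol 11.1 lists a two-year limit only for pralatrexate. The stop date for an observation patient who reaches two years therefore needs to be stated.
4. Reconcile the end of safety follow-up between Protocol 7.3, including its provision for unresolved related AEs, and SAP 3, so that the on-study flag has one meaning.

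The cost is SAP wording and one more table column. Protocol 10.7.2, 11 and 14.3.1 already call for AEs and discontinuation reasons in both arms, and the shells are still to be written. The one drawback is that the two arms' windows start from different anchors, which a footnote should state.

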11 APPENDICES

11.1 Table/Figure/Listing Shells

Table, listing, and figure shells will be provided in a separate document prior to final analysis of study data.

11.2 Reference Values/Severity Grades

Severity grades for AEs are provided by the investigator. Severity grades for laboratory values will be derived programmatically based on the CTCAE grading scale – Version 4.0. For laboratory values requiring a clinical assessment for determination of severity, severity will not be derived programmatically.

11.3 Handling of Dates, Incomplete Dates, and Missing Dates for Adverse Events and Concomitant Medications

Imputation Rules for Partial or Missing Stop Dates

If a partial or complete stop date is present and the “ongoing” or “continuing” box is checked, then it will be assumed that the AE or concomitant medication stopped and the stop date will be imputed if partial.

Imputation Rules for Partial or Missing Start Dates for AEs and Concomitant Medications

Several different date variables are kept in the standard analysis datasets for AEs and concomitant medications because the start and stop dates may be incomplete and data processing requires different assumptions about incomplete dates for different purposes.

The standard AE analysis datasets have the following date variables:

aestdc – character variable for AE start date. It may be partial date (eg, 20MAY07, MAY07, 07)

aestdt – numeric date variable for AE start date. Missing for partial date.

aefstdt – first possible AE start date. For missing day of month, set to first day of month. For missing month, set to first day of year. For missing year, set to missing value.

aespdc – character variable for AE stop date. May be partial date. (See aestdc above.)

aespdt – numeric date variable for AE stop date. Missing if partial date.

aelspdt – last possible AE stop date. For missing day of month, set to last day of month. For missing month, set to last day of year. For missing year, set to missing value.

Aestrsp - first possible AE start date minus the treatment stop day. Positive values are the number of days the AE started after treatment stopped and are used to set post-treatment cutoffs.

Aestdc and aespdc are used for the main AE listings. Aefstdt and aelspdt are used for ordering records in chronological order.

The standard concomitant medication analysis datasets have the following date variables:

cmstdc – character variable for concomitant medication (CM) start date. May be partial date (eg, 20MAY07, MAY07, 07)

cmstdt – numeric date variable for CM start date. Missing for partial date.

cmfstdt – first possible CM start date. For missing day of month, set to first day of month. For missing month, set to first day of year. For missing year, set to missing value.

cmlstdt – last possible CM start date. For missing day of month, set to last day of month. For missing month, set to last day of year. For missing year, set to missing value.

cmspdc – character variable for CM stop date. May be partial date. (See cmstdc above.)

cmspdt – numeric date variable for CM stop date. Missing for partial date.

cmfspdt – first possible CM stop date. (See cmfstdt above.)

cmlspdt – last possible CM stop date. (See cmlstdt above.)

cmstrsp – first possible CM start date minus the treatment stop day. Positive values are the number of days the CM started after treatment stopped and are used to set post treatment cutoffs.

Cmstdc and cmspdc are used for the main CM listings. Cmfstdt and cmlspdt are used for ordering records in chronological order.

11.4 Preferred Terms for Adverse Events Grouped by Similar Preferred Term

Listed in Table 11.1 below are the AEs identified for the pralatrexate program. The AEs grouped by similar preferred term are evolving over time as the coding dictionary is updated (there could be changes to the already identified events) and as the pralatrexate program expands (additional AEs may be added and others may be removed). AEs included in the data summary will be based on the current list identified by the clinical study team at the time of the analysis.

Table 11.1. Adverse Events Grouped by Similar Preferred Term

Category	Preferred Term
Mucosal Inflammation	Mucosal inflammation Stomatitis Anal Inflammation Mucositis Anal Vaginal Inflammation Rectal Mucositis Esophagitis Mouth Ulceration Oral Mucosal Erythema Oesophagitis Gingivitis Balanoposthitis Pharyngeal Inflammation Pharyngitis Stomatitis Haemorrhagic
Thrombocytopenia	Thrombocytopenia Platelet Count Decreased
Anemia	Anemia Hemoglobin Decreased
Hypokalemia	Hypokalemia Blood Potassium Decreased
Neutropenia	Neutropenia Neutrophil Count Decreased
Dermatitis Exfoliative	Dermatitis Exfoliative Exfoliative Rash
Rash	Rash Dermatitis Acneiform Rash Maculo-papular Rash Macular Rash Papular Dermatitis

Category	Preferred Term
	Dry Skin Rash Erythematous Skin Disorder
Liver Function Test Abnormal	Liver Function Test Abnormal Alanine Aminotransferase Increased Alanine Aminotransferase Aspartate Aminotransferase Aspartate Aminotransferase Increased Transaminases Increased
Oedema	Oedema Oedema Peripheral Pitting Oedema
Dry Mouth	Dry Mouth Lip Dry Dry Throat
Dyspepsia	Dyspepsia Gastritis Gastrooesophageal Reflux Disease
Odynophagia	Odynophagia Oesophageal Pain
Pruritus	Pruritus Pruritus Generalized
Anorexia	Anorexia Decreased Appetite
Leukopenia	Leukopenia White Blood Cell Count Decreased

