1 INTRODUCTION

The purpose of this statistical analysis plan is to provide details of the statistical analyses that have been outlined within version 2.1 of the protocol for pralatrexate study PDX-017 dated 31 Oct 2011. The scope of this plan includes the interim and final analyses. The analyses detailed within this plan will help to evaluate the efficacy and safety of pralatrexate as sequential therapy in patients with peripheral T-cell lymphoma (PTCL) who have achieved an objective response following initial treatment of first-line cyclophosphamide, doxorubicin, vincristine, and prednisone (CHOP)-based regimen.

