3 STUDY DESIGN

This is an international, multi-center, randomized, Phase 3, open-label study of sequential pralatrexate versus observation in patients with previously undiagnosed PTCL who have achieved an objective response following initial treatment with CHOP-based chemotherapy.

Upon documentation of an objective response following at least 6 cycles of a designated CHOP-based chemotherapy, confirmation of histopathology by independent review, and confirmation that all eligibility criteria are met, patients will be randomized in a 2:1 ratio to either pralatrexate or observation, according to a permuted block design (block sizes of 3) stratified by response per investigator at completion of CHOP-based therapy (complete response [CR] vs partial response [PR]).

Patients randomized to the Pralatrexate Arm will receive pralatrexate as an intravenous (IV) push administration over a minimum of 30 seconds up to a maximum of 5 minutes via a patent free-flowing IV line containing normal saline (0.9% sodium chloride [NaCl]) weekly for 3 weeks (\pm 1 day at each time point) of a 4-week cycle. The initial dose of pralatrexate will be 30 mg/m² which, based on protocol-defined criteria, may be reduced to 20 mg/m² with potential further reduction to 15 mg/m² and 10 mg/m². There will be sparse sampling for pharmacokinetics (PK). Pralatrexate will continue to be administered until a criterion for study treatment discontinuation is met or up to a maximum of 2 years.

Patients randomized to the Observation Arm will remain under observation, attend clinic visits every 4 weeks, and receive a follow-up phone call from a healthcare professional during each week 2 of 4 until a criterion for study treatment discontinuation is met for a maximum of 2 years.

All patients will receive vitamin supplementation, consisting of vitamin B₁₂ 1 mg intramuscularly (IM) every (q) 8-10 weeks and folic acid 1-1.25 mg by mouth (po) once a day (qd). Vitamin supplementation will begin at least 7 days prior to the projected initiation of pralatrexate/observation and continue throughout the study until the Initial Follow-up Visit.

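### Membership of the grouped adverse-event categories is left to the study team at the time of analysis in an open-label trial; freeze and version the list (minor)

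*SAP*

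**What the plan says.** SAP 11.4 gives 15 categories in Table 11.1, each with its member preferred terms. It then describes the groupings as "evolving over time as the coding dictionary is updated" and as the pralatrexate program expands, noting that "additional AEs may be added and others may be removed". Its closing sentence sets the operative rule: the events summarized are "based on the current list identified by the clinical study team at the time of the analysis".

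SAP 8.6 adds a second route to change: "additional preferred terms may be identified within each category during data review and added to this list". Protocol 15.8.2 carries the same permission and refers to the SAP for the list itself.

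Three other statements set the context:
- **Design (SAP 3):** "This is an international, multi-center, randomized, Phase 3, open-label study of sequential pralatrexate versus observation".
- **Who watches the data (SAP 8.6):** "Study data will be monitored on an ongoing basis by the clinical study team".
- **Scope (SAP 1):** "The scope of this plan includes the interim and final analyses".

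SAP 3.3 places a DMC safety evaluation at about 100 patients and another at each interim efficacy analysis.

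**The concern.** A grouped category is a composite, and its rate depends on which terms are in it. Some categories in Table 11.1 leave little room for judgement, such as thrombocytopenia paired with decreased platelet count. Others leave a good deal. Mucosal Inflammation includes gingivitis and pharyngitis, and Rash includes dry skin and an unspecific skin-disorder term. Terms of that kind can plausibly occur in both arms for reasons unrelated to the drug, so including or leaving out one of them changes the comparison.

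The team that may settle membership at analysis time also follows the accruing data of an open-label trial. A choice made in good faith could still be shaped by knowing which patients, in which arm, reported a term. Nothing stops the list used at one look from differing from the list at the next. At stake are the credibility of the grouped toxicity summaries and their comparability across looks.

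**Working it through.** There is no planned figure to reproduce, because no sample size, alpha or event count depends on this list. The check is a reading of the text plus a small illustration.

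**Text check.** I compared SAP 11.4 with SAP 1, 3, 3.3, 8.6 and 9 and with Protocol 15.8.2, looking for four safeguards.

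| Safeguard | Found? |
|---|---|
| Freeze date for the list | No; SAP 11.4 points to the time of analysis |
| Terms chosen without treatment assignment | No |
| Version record, with a duty to report departures from Table 11.1 | No |
| Same list at interim and final analyses | No |

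The three places also differ in what they permit. SAP 11.4 allows additions and removals, and ties these to program expansion. SAP 8.6 and Protocol 15.8.2 allow additions only, within a category, but do not limit the reason to dictionary updates or program expansion.

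**Illustration.** All incidences are assumed, because the documents give none. Suppose the composite without the disputed term occurs in 60% on pralatrexate and 5% on observation. Suppose also that the term occurs independently of the rest, with incidence b in both arms. Then composite incidence with the term = 1 − (1 − p)(1 − b).

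For b = 10%:
- Pralatrexate: 1 − 0.40 × 0.90 = 0.640
- Observation: 1 − 0.95 × 0.90 = 0.145
- Risk difference: 64.0 − 14.5 = 49.5 points, against 60 − 5 = 55.0 points without the term

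With equal background in both arms, the difference is simply multiplied by (1 − b): 55.0 × 0.90 = 49.5.

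Range over b:

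| b | Pralatrexate | Observation | Risk difference (points) |
|---|---|---|---|
| Term left out | 60.0% | 5.0% | 55.0 |
| 5% | 62.0% | 9.75% | 52.25 |
| 10% | 64.0% | 14.5% | 49.5 |
| 15% | 66.0% | 19.25% | 46.75 |

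Read upward, the same table shows the effect of dropping such a term from the list. A term that is itself commoner on pralatrexate does little. With a composite of 50% versus 5%, adding a term at 5% versus 2% takes the difference from 45.0 to 45.6 points (52.5% versus 6.9%).

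**The case against.** The strongest defence is that little depends on these tables. The safety endpoints in SAP 4.3 are treatment-emergent adverse events and laboratory changes; no grouped category is an endpoint and none is tested. Ungrouped tables by system organ class and preferred term, together with full listings, are planned beside the grouped ones, so a reader can regroup the terms. Cytopenias and liver abnormalities are also covered by laboratory summaries whose grades are derived programmatically (SAP 8.6 and 11.2), except where a clinical assessment is needed, and the list does not touch these. Dictionary updates are a legitimate reason to revise a list. All of this stands, and it is why the point is minor. It does not supply a prespecified definition of the groups.

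Several stronger readings are tempting but not supported:

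- **That these are the trial's main toxicity results.** Nothing in the documents gives them that standing.
- **That discontinuation events will be seen only in grouped form.** Table 9.1 might suggest this, since its one such entry is "Treatment-emergent AEs Grouped by Similar Preferred Term Leading to Treatment Discontinuation". But SAP 8.6 and Protocol 15.8.1 plan discontinuation events by preferred term, and Table 9.2 lists them by patient. The grouped table covers the Pralatrexate Arm only, so it contains no between-arm contrast.
- **That terms may be removed because of this trial's data.** Removals are linked to program expansion; the data-review permission covers additions only.
- **That the team will see aggregate interim results by arm.** SAP 3.3 has the DMC perform the interim analyses. The exposure comes from open-label patient-level data and ongoing monitoring.
- **That DMC looks will be non-comparable.** The documents do not say the DMC uses the grouped tables, and earlier looks can be retabulated from the retained preferred terms.
- **That relative toxicity could be rewritten.** In the 10% example the risk ratio falls from 12.0 to 4.4, but the SAP plans incidence by arm, not risk ratios for adverse events, and a ratio on an assumed 5% control rate is inherently unstable. Rates of 64.0% versus 14.5% would lead to the same clinical conclusion as 60% versus 5%.

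**Conclusion.** The point holds as a minor one. The grouped adverse-event categories are printed but not prespecified: the list can be settled at analysis time by a team with access to open-label data, and nothing requires the same list at each look. The illustration suggests a shift of a few points in a large risk difference per disputed term (2.75 to 8.25 points for backgrounds of 5% to 15%). That size rests on assumed incidences, independence and equal background in both arms. PFS, OS, alpha and power are unaffected, and no event would disappear from the ungrouped output. The case for acting is that the change is nearly free now, whereas a list settled after the data have been seen cannot credibly be made prespecified.

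**What to change.** Replace the last sentence of SAP 11.4 with a rule to this effect:

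- Table 11.1 is the primary grouping.
- Any additions are made from the pooled term list without treatment assignment.
- The list is dated and frozen, with its MedDRA version, before the first formal DMC safety review (about 100 patients), or at the latest before the data cut-off for the first PFS/OS analysis.
- The frozen list is used unchanged at later analyses, apart from mapping MedDRA renames.
- Terms identified later appear in a supplementary grouped table labelled post hoc, with changes from Table 11.1 reported.

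Remove the data-review permission from both SAP 8.6 and Protocol 15.8.2, so that neither conflicts with the revised 11.4. The earlier freeze is preferable. The first PFS/OS analysis is expected about 48 months after the first randomization; by then the team will have followed open-label data for years, and a review without treatment assignment would protect less.

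The cost is a few sentences in each document and one term review. The downside is that terms recognized late appear only in the supplementary grouped table and the ungrouped tables.
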